4.7. Cohort Follow up and Clinic Visits

All subjects will be seen by the study physician at the time of randomization. From that point forward throughout the trial, all participants will be required to see a member of the randomizing physician's study team at least once every 4 months in addition to the regularly scheduled laboratory and symptom monitoring procedures described below. At those visits, compliance (measured by pill count) as well as evidence of side effects will be ascertained by self-report, and in the absence of a study endpoint or laboratory abnormality, a new 4-month supply of study drug (or blinded placebo) provided. A Patient Contact Information Form will be updated at each of these 4-month visits to facilitate long-term follow-up.

Cohort follow-up will include a visit form filled out at each of these appointments. Information will similarly be sought concerning trial endpoints, issues of compliance will be

reviewed, anthropometric measures and brief physical examination including reassessment of physical function will be performed, participant questions answered, the drug supply ensured, and any outstanding study forms completed and/or updated. In addition, signs or symptoms of early drug toxicity will be assessed, as well as the occurrence of any primary or secondary trial endpoints or other clinical events of interest. Nephropathy, a clinical event of interest, will be assessed by collecting urine for albumin and creatinine at 8 months, 12 months, and then every 6 months after randomization. Since these data will be obtained in an identical manner from participants randomly allocated to LDM as well as to placebo, this procedure will also provide a mechanism for monitoring by the Data Coordinating Center (DCC) and reports to the Data and Safety and Monitoring Board (DSMB) of any differences between treatment groups with regard to side effects or efficacy. At each regularly scheduled safety lab visit (once a month for the first 6 months after randomization, then at least bi-monthly), participants will be asked about clinical symptoms and side effects of the study medication so that study drug dosage may be adjusted or temporarily stopped if necessary. In order to better understand the toxicities of methotrexate, at 6 months a blood sample will be collected for the measurement of key metabolites of methotrexate.

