4.14. Drug Compliance Monitoring

The primary measure of compliance will be based on the return of calendar packs to the physician at each of the 4-month office visits (at which time new calendar packs will be issued as long as no trial endpoint or major side-effects have occurred).

As an additional measure of compliance, washed packed red blood cells collected 6 months after randomization will be stored in a central laboratory for measures of methotrexate levels. This will be done using a methotrexate polyglutamate assay that provides a semi-quantitative method of evaluating methotrexate absorption and metabolism. The results of this assay will not be available to blinded study staff until after the study has completed and the database has been locked.

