4.15. Central Laboratory and Bio-bank

Blood samples for storage in a bio-bank at Brigham and Women's Hospital will be obtained at the pre-run-in, randomization, and at 8 and 24 months after randomization. Processing and long-term storage of these samples will be done in a liquid nitrogen biobank facility in Boston, which has been used for this purpose in multiple prior NIH-funded trials and large cohort studies. White blood cells from the pre-run-in sample will also be stored in this facility to allow for DNA extraction at a later date. As described in the informed consent documents, participation in the genetic bio-banking portions of CIRT will be on an "opt-out" basis and are not a requirement for participation in the main trial.

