Additional planned exploratory and mechanistic analyses include evaluation of whether treatment effects vary across categories of baseline covariates including age, gender, race, presence of diabetes or metabolic syndrome at baseline, baseline lipid levels, baseline inflammatory biomarker levels including high-sensitivity C-reactive protein, revascularization status, baseline background treatments which affect adenosine function, and nutritional measures related to adenosine function such as estimated daily total caffeine intake. Clinical endpoints of interest that will be prospectively evaluated include incident age-related macular degeneration, sleep apnea, and nephropathy and retinopathy. Analyses are planned that will evaluate the effect of LDM as compared to placebo on a series of inflammatory biomarkers (hsCRP, IL-6, and others); evaluate whether common genetic variants associated with vascular risk, inflammation, thrombosis, or LDM metabolism modify any benefits of LDM; and evaluate the effect of LDM as compared to placebo on indices of diabetes progression (among those with baseline diabetes).

Mediation analyses exploring treatment effect differences by plasma measures of LDM metabolism, by reported LDM adherence, and by achieved reduction in inflammation, are also planned. Longitudinal analyses will quantify the impact of LDM on lipid levels, biomarkers of inflammation, and change in HbA1c, with the latter analyses stratified by presence of diabetes at baseline. Analyses will also evaluate whether genetic polymorphisms associated with vascular risk, inflammation, thrombosis, or LDM metabolism modify any benefits or risks of LDM on clinical outcomes observed in the trial.

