While all primary and secondary endpoint analyses are on an intention-to-treat basis, CIRT is also functioning as a proof of concept trial and thus secondary analyses of those compliant with the respective LDM or placebo regimens will also be conducted. These analyses will use time-varying proportional hazards models, with an individual's level of adherence updated at each study visit. Adherence will be examined on a time-varying basis using a metric based on percent of study drug taken at last visit, such as half or more vs. less than half, and will also be analyzed cumulatively. Similar analyses will also be conducted on the basis of plasma levels of LDM metabolism.

We will explore in subgroup analyses whether treatment effects vary across categories of baseline covariates including age, gender, race, presence of diabetes or metabolic syndrome at baseline, index MI ≤ 6 vs > 6 months prior, baseline lipid levels, CHF at baseline, baseline inflammatory biomarker levels including high-sensitivity C-reactive protein, revascularization status, baseline background treatments including those known to affect adenosine, such as aggrenox, methylxanthines, and fioricet, nutritional measures related to adenosine function such as estimated daily total caffeine intake, and by plasma measures of LDM metabolism. Cutpoints for analyses will be determined after the final distribution of patients has been established.

Within each subgroup, we will use proportional hazards models to estimate the relative rate of the primary endpoint associated with active treatment versus placebo. Both crude analyses and models including limited baseline covariates will be fitted. To test for the significance of modification of treatment effects by a baseline characteristic, we will include interaction terms between this characteristic and treatment in the proportional hazards model, with statistical significance determined by a likelihood ratio test comparing models with and without the interaction terms between treatment and the categories of a specific covariate.

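### SAP 4.3 plans time-updated, cumulative and subgroup analyses on plasma levels of LDM metabolism, but the protocol specifies only one methotrexate assay, on red cells at 6 months

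*Combined protocol and SAP*

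**What the plan says.** SAP 4.3 (Efficacy) supplements the intention-to-treat analysis with analyses of compliant participants. It specifies the model: "These analyses will use time-varying proportional hazards models, with an individual's level of adherence updated at each study visit". Adherence is the percentage of study drug taken, for example half or more against less than half, and is also to be analysed cumulatively. The next sentence extends this to drug levels: "Similar analyses will also be conducted on the basis of plasma levels of LDM metabolism".

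The same measure appears twice more in the SAP. Section 1.1 plans "Mediation analyses exploring treatment effect differences by plasma measures of LDM metabolism". The subgroup paragraph of 4.3 puts plasma measures of LDM metabolism at the end of its list of baseline covariates, to be tested by treatment interaction.

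The protocol describes the measurement in 4.14 (Drug Compliance Monitoring): "washed packed red blood cells collected 6 months after randomization will be stored in a central laboratory for measures of methotrexate levels". On the method it says: "This will be done using a methotrexate polyglutamate assay that provides a semi-quantitative method of evaluating methotrexate absorption and metabolism". Protocol 4.7 adds that "at 6 months a blood sample will be collected for the measurement of key metabolites of methotrexate", and 4.9 repeats this for all participants; neither section names a matrix. Bio-bank blood under 4.15 "will be obtained at the pre-run-in, randomization, and at 8 and 24 months after randomization", with no methotrexate assay assigned to it. Both protocol versions in the combined document carry the same text on these points, so the mismatch does not come from an amendment.

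**The concern.** The SAP and the protocol differ on what is measured and on how often. The SAP says plasma and refers back to a model that needs a value at each visit. The protocol says red cells, once.

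This is more than a missing detail. The analysis as written cannot be run, so whoever runs it must invent a substitute: carry the 6-month value forward, carry it back to randomization, or assay stored samples that were not planned for this purpose. These choices can give different answers.

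The assay is the only laboratory check on compliance that the protocol describes; the primary measure is pill count. SAP 4.3 justifies the compliance analyses by calling the trial a proof of concept. The introduction placed before the SAP reports that the trial stopped on a futility boundary and on absence of evidence for a reduction in hsCRP. Whether participants took and absorbed the drug therefore bears on how a null result is read. Protocol 4.14 withholds the assay results from blinded staff until after database lock, so the rule for using them can be fixed before they are seen.

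**Working it through.** **1. Required against available measurements**

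| | SAP requires | Protocol supplies |
|---|---|---|
| Matrix | plasma (SAP 1.1, 4.3) | washed packed red cells (4.14); not named (4.7, 4.9) |
| Frequency | each study visit, and cumulative (SAP 4.3) | once, at 6 months |
| Timing for subgroup use | baseline covariate (SAP 4.3) | 6 months after randomization |
| Arms | interaction with treatment (SAP 4.3) | a drug level is informative on LDM only |

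**2. Number of updates.** Protocol 4.7 requires visits at least every 4 months. SAP 1.3 takes follow-up as 2 to 4 years for participants who are not censored and have no event. That gives 24/4 = 6 to 48/4 = 12 adherence updates per participant at the minimum visit frequency, against 1 scheduled methotrexate assay. The bio-bank schedule would add at most two post-randomization points (8 and 24 months), and only if an assay were assigned to it.

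**3. Events before the value exists.** Inputs from SAP 1.3:
- 3,500 participants per arm
- placebo rate 3.25 to 4.0 per 100 person-years
- 25% reduction on LDM
- 5% annual loss
- follow-up of 2 to 4 years

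With hazard λ and m = λ + 0.05, the expected events per arm are:

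- whole trial: 3500 × (λ/m) × {1 − [exp(−2m) − exp(−4m)]/(2m)}
- before month 6: 3500 × (λ/m) × {1 − exp(−0.5m)}

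The second formula needs no entry-time term because everyone has at least 2 years of potential follow-up.

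| Placebo rate | λ placebo, LDM | Whole trial (placebo + LDM) | SAP states | Before month 6 (placebo + LDM) | Share |
|---|---|---|---|---|---|
| 3.25 | 0.0325, 0.024375 | 301.08 + 228.55 = 529.6 | 529 | 55.72 + 41.87 = 97.6 | 18.4% |
| 4.0 | 0.0400, 0.0300 | 366.47 + 278.95 = 645.4 | 645 | 68.45 + 51.46 = 119.9 | 18.6% |

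The model reproduces the SAP's own event totals. It then puts 18% to 19% of primary events before any drug level exists. In the LDM arm alone, where a landmark analysis would be done, these are about 42 of 229 (18.3%) to 51 of 279 (18.4%) events.

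**4. Subgroup use.** An interaction test compares the treatment effect across levels of a characteristic that both arms have before treatment can affect it. A 6-month methotrexate level is a consequence of assignment, adherence and metabolism. Samples are taken from placebo participants too, but they are not on the drug, so they cannot be placed at the same levels as LDM participants. There is no placebo comparator within a level, and the interaction has no interpretation.

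**The case against.** The strongest reply is that plasma levels of LDM metabolism is loose wording for the 6-month assay. The phrase sits close to the protocol's language about absorption and metabolism and about key metabolites. This reading is plausible, and on it the matrix conflict disappears. What remains is that a single value cannot be "with an individual's level of adherence updated at each study visit" or cumulated.

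A second reply is that a time-varying Cox model can let a covariate enter when it is measured, so nothing commits the SAP to using the value from time zero. This stands. The early-event share shows what would be exposed to that error, not an error that the SAP has planned. But a covariate that enters once, at month 6, is in effect a landmark analysis, and the SAP should say so.

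A third is that the subgroup sentence could be parsed with the LDM measure as a separate item outside the baseline covariates. That does not help: the measure is still post-randomization and uninformative on placebo.

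A reader might go further and infer that plasma sampled without regard to the weekly dose would label most adherent participants as off drug. The documents do not support this. It needs a plasma half-life, a detection limit, an off-drug cut-off and the interval from dose to draw. None is given, and protocol 3.4 states the route of elimination, not its rate. Nor does any section plan a methotrexate assay on the stored 8- and 24-month blood.

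**Conclusion.** The point holds in a limited form. The drug-level analyses in SAP 4.3 cannot be carried out as described, because the protocol specifies one methotrexate assay at 6 months and the SAP calls for a series. The measure also does not belong among baseline covariates for treatment-interaction tests. Both conclusions rest on the text alone and hold whichever matrix was meant.

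The size is conditional. If the value were applied from randomization, the follow-up containing about 18% to 19% of primary events would be classified by a later measurement and conditioned on surviving to be sampled. That figure assumes the SAP's event rates, 25% reduction, 5% annual loss and 2 to 4 years of follow-up.

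The severity is minor. The analysis is secondary. The primary analysis, its alpha and power, the stopping rules and the pill-count adherence analyses do not depend on it.

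**What to change.** In SAP 1.1 and 4.3:

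- Name the analyte as the 6-month red-cell methotrexate polyglutamate result of protocol 4.14, in place of plasma levels or measures.
- Analyse it as one landmark exposure among LDM-arm participants who are event-free at the draw. Start follow-up at the draw, adjust for baseline covariates, and report it as a non-randomised comparison, since level reflects adherence and patient characteristics as well as drug effect.
- State the level categories before the results are released.
- Drop the time-updated and cumulative versions for this measure.
- Remove it from the list of baseline covariates for treatment-interaction tests.
- Optionally, compare it with the pack-count adherence category for the interval that contains month 6.

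Leave the pill-count adherence analyses unchanged in both arms.

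The cost is SAP wording; the sample is already in the protocol. The statistical price is that events before month 6, about 18% of those expected in the LDM arm, leave this one secondary analysis.

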Another perspective on sample size estimation based on the above formulation of enrollment indicates that, regardless of the rate of major cardiovascular events in the placebo group, the trial must accrue 514 total confirmed major cardiovascular events in order to have 90% power to detect a 25% reduction in this rate, based on a two-sided test with $\alpha=0.05$. Given a conservative interim monitoring plan such as that described below, then the approach of Reboussin et al² indicates that sample size needs to be increased by 1.9% to maintain 90% power in the presence of monitoring. We therefore stipulate that the trial will require accrual of 530 total primary events. With respect to the above assumptions on accrual and drop out, and the range of event rates in the placebo group shown in the above table, the proposed trial with 7,000 randomized subjects would be expected to accrue between 529 endpoints (placebo event rate=3.25/100 person-years) and 645 endpoints (placebo event rate=4.0/100 person-years) under the assumption of a 25% reduction in hazard associated with methotrexate.

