4.3. Efficacy

Efficacy analyses of the primary and secondary endpoints of the trial will focus on time from randomization to the first occurrence of the event. These analyses will use a likelihood ratio test based on a proportional hazards model stratified on time since index myocardial infarction (≥ 6 months vs < 6 months) and diabetes mellitus vs metabolic syndrome alone at baseline, to test the null hypothesis of no association between assignment to active methotrexate and the rate of the endpoint. Estimation will use the exact method to handle ties⁴. Although randomization is also stratified by site, we judge the potential loss of information associated with additional stratification on this variable to be a greater concern than any associated gain, so that stratification by site will not be part of the primary analysis. All primary and pre-specified secondary analyses will classify patients according to their randomized treatment assignment, i.e. according to the intention to treat principle, and will base evaluation of statistical significance on a two-sided test with level 0.05. The estimated relative hazard in the methotrexate group compared to the placebo group with an accompanying 95% confidence interval will quantify the treatment effect⁵. If this relative hazard is less than 1, then $100 \times (1 - \text{estimated relative hazard})$ will be defined as the percent reduction in hazard associated with methotrexate treatment.

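### Effect modification by hsCRP and other continuous baseline measures is tested only in categories, which costs about 35-41% of effective information if the interaction is log-linear; separately, cutpoints are not tied to unblinding.

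*Combined protocol and SAP*

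**What the plan says.** SAP 4.3 (Efficacy) opens its subgroup paragraph with "We will explore in subgroup analyses whether treatment effects vary across categories of baseline covariates including age, gender, race". The list goes on to lipid levels, "baseline inflammatory biomarker levels including high-sensitivity C-reactive protein", and caffeine intake, among others. Significance of effect modification is judged by a "likelihood ratio test comparing models with and without the interaction terms between treatment and the categories of a specific covariate". Current protocol 5.7 (Subgroup Analyses) specifies the same test and a similar list.

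On cutpoints, SAP 4.3 says only: "Cutpoints for analyses will be determined after the final distribution of patients has been established". It gives no number of groups and no quantile rule, and it does not say whether the choice precedes unblinding. Neither document plans an interaction with a covariate kept continuous.

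SAP 1.1 describes the status of this work: "Additional planned exploratory and mechanistic analyses include evaluation of whether treatment effects vary across categories of baseline covariates". SAP 4.3 adds that subgroup results will be interpreted very cautiously and in light of the overall effect.

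**The concern.** hsCRP, lipids, age and caffeine intake are measured on a continuous scale. Grouping them discards the variation within groups. With three or more groups, the likelihood ratio test also spends extra degrees of freedom on a question that may be a simple gradient. Interaction tests have low power to begin with, so the loss matters.

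The protocol's own background (3.1) notes that, in an earlier statin trial, the largest absolute risk reduction was seen in those with the most persistent inflammatory response. Whether the benefit rises with baseline inflammation is a graded question of that kind, and the planned test may miss a gradient that a continuous term would find.

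The open cutpoints are a different problem. They cost no information, but they leave a choice that can change the result and is not documented as having been made blind. Protocol 4.17 refers to unblinded staff at the Data Coordinating Center, and nothing says that whoever sets the cutpoints must be blinded.

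**Working it through.** **Inputs from the documents.** Before allowing for monitoring, "the trial must accrue 514 total confirmed major cardiovascular events in order to have 90% power to detect a 25% reduction in this rate" (SAP 1.3); then "We therefore stipulate that the trial will require accrual of 530 total primary events". For primary and pre-specified secondary analyses the SAP "will base evaluation of statistical significance on a two-sided test with level 0.05"; I assume the same level for the interaction test. Allocation is 1:1 (SAP 1.2).

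**Assumptions not in the documents.** The modifier is normal (after logging if skewed), the log hazard ratio is linear in it, and groups are of equal size. The interaction sizes are illustrative.

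**Step 1: reproduce the plan's figure.** (1.960 + 1.282)² = 10.51.
- Freedman: 10.51 × (1.75/0.25)² = 515 events.
- Schoenfeld: 4 × 10.51/(ln 0.75)² = 508 events.

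Both are close to 514. Then 514 × 1.019 = 524, which the plan sets at 530. SAP 5.2 itself uses Z = log(HR)√(D/4), so a variance of 4/D is the plan's own basis. The documents give no power figure for any interaction test.

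**Step 2: continuous term.** Let γ be the log ratio of hazard ratios per SD. Its SE is 2/√D and the noncentrality is γ²D/4 on 1 df. For 0.80 per SD and D = 530, this is (0.2231)² × 132.5 = 6.60, which gives 73% power.

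**Step 3: categories.** Grouping keeps only the between-group share of the modifier's variance, so the noncentrality is share × γ²D/4, on k−1 df.

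| | Share kept | Power, 0.90 per SD | Power, 0.80 per SD | Power, 0.75 per SD |
|---|---|---|---|---|
| Continuous, 1 df | 1 | 23% | 73% | 91% |
| 2 groups, 1 df | 2/π = 0.637 | 16% | 54% | 75% |
| 3 groups, 2 df | 0.793 | 15% | 52% | 76% |
| 4 groups, 3 df | 0.861 | 14% | 49% | 73% |

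**Step 4: effective information at 80% power.** The noncentrality needed for 80% power is 7.85, 9.63, 10.90 and 11.94 on 1 to 4 df. Effective information is share × 7.85/needed.
- 2 groups: 0.637, a 36% loss.
- 3 groups: 0.793 × 7.85/9.63 = 0.646, a 35% loss.
- 4 groups: 0.861 × 7.85/10.90 = 0.620, a 38% loss.
- 5 groups (share 0.897): 0.897 × 7.85/11.94 = 0.590, a 41% loss.

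On share alone, the losses are 36%, 21%, 14% and 10%. From three groups up, the degrees of freedom bring the effective loss back above a third.

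**Step 5: simulation check.** 600 runs of 7,000 participants with about 603 events and a ratio of 0.784 per SD gave 86% power continuous, 65% for a median split, 67% for tertiles and 61% for quartiles.

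**Step 6: sensitivity.**
- Unequal two-way splits lose more: 41% at 67/33 and 46% at 75/25.
- A uniform modifier loses less: 25% of information with a median split, and 11% with tertiles before the df cost.
- If the true modification is a step at the median, the order reverses and the linear term loses 36%.
- At 265 events (half of target) and 0.75 per SD, power is 65% continuous against 46%, 45% and 42% for two, three and four groups.

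**The case against.** The other side has five good arguments.

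1. The documents never say that covariates will be split in two, or give any number of groups. The loss is therefore not a fact about the plan but a consequence of assumptions about shape and distribution. This stands, and every figure above is conditional on them.
2. The linear term is not uniformly better. Under a step or a non-monotone pattern it can do worse than categories. This also stands, and it is why the categorical analysis should be kept alongside.
3. The larger power gaps use large interactions. With an average hazard ratio of 0.75, a ratio of 0.75 per SD means 0.75/0.75 = 1.00 at one SD below the mean and 0.75 × 0.75 = 0.56 at one SD above. At 0.90 per SD no form of the test is adequate. This stands as a limit on what the change can deliver.
4. Cutpoints are tied to the distribution of patients, not to outcomes, and quantile cutpoints need that distribution too. This largely stands. What is missing is a named rule and a statement that it is applied before unblinding.
5. The analyses are exploratory, with cautious interpretation promised. This stands as a limit on the consequences, but it is no reason to choose the less efficient test of a graded question.

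A reader might also infer that choosing cutpoints late is what loses the information. It is not: categorizing does that, and timing is a separate matter of flexibility. Nor do the documents support treating the hsCRP subgroup test as the key test of the inflammatory hypothesis. The randomized primary comparison tests that directly, and a constant hazard ratio across hsCRP would be compatible with it. The planned analysis by achieved reduction in inflammation (SAP 4.3) does not fill the gap, because it uses post-randomization levels.

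**Conclusion.** The concern holds in conditional form. For a roughly normal modifier with a log-linear interaction and two to five equal groups, the planned test gives up about 35-41% of effective information at 80% power. At 530 events and 0.80 per SD, that is 73% power against 49-54% for two to four groups. A flat statement that the plan discards over a third of the information goes too far: the raw share lost is 36% only for a median split, and a true step at the cut would favour the categories.

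The missing link between cutpoints and unblinding is a second, smaller gap, and nothing in the documents suggests that cutpoints would be chosen on outcomes. No primary or secondary conclusion depends on either point. The change is worth making because it costs almost nothing and improves the test for the most natural form of effect modification.

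**What to change.** In SAP 4.3, with a matching sentence in protocol 5.7:

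- For each continuous baseline modifier, hsCRP above all, name a 1-df treatment × continuous covariate term in the proportional hazards model as the main interaction test, with skewed markers on the log scale.
- Use the pre-run-in value for biomarkers. Protocol 4.15 banks blood both before the run-in and at randomization, and the randomization sample follows open-label methotrexate (4.5).
- Add a spline in the covariate by treatment as a check on shape.
- Keep the categorical estimates and their likelihood ratio test for display and as a supporting analysis. State the number of groups, and define cutpoints as quantiles of all randomized participants, fixed before treatment codes are released.

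The cost is SAP and protocol wording; no new data are needed. The downside is that the linear term is less efficient if the true modification is a step or non-monotone. The spline and the retained categorical analysis are there to show that.
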